4.2 Data collection and data management for model optimization phase

4.2.1 Formative research and programme learning

Information on the different data collection activities during the formative research is outlined above. Instruments, or semi-structured discussion guides, for the different activities will be developed guided by barriers and facilitators learned from the iKMC trial³⁰ and the scale-up KMC study²⁹. We will also explore the feasibility of proposed activities. All instruments will be reviewed and adapted by the study teams in each site and translated and tested prior to data collection, as part of training of the research teams.

Women who had a preterm or LBW baby in a study facility will be interviewed to understand personal journeys, and barriers and facilitators to receiving care for their babies, particularly for KMC and for starting KMC immediately after birth, their experience of the care received during their stay in the facility as well as support needed after discharge from the facility to care for their baby. We will use a gender and intersectionality analysis approach to understand how gender relations and power dynamics within the household, community and encounters with health workers influence a woman's decisions about care and her experience of receiving care for a preterm or LBW baby's birth and the support she needs to continue providing care in the home. This will provide us with a holistic understanding of an individual woman's care pathway from the home, through different levels of facility-based care, and potential power dynamics that may need to be addressed in the implementation strategy.

We expect about 20-30 women will be interviewed only once and the interview will take no longer than one hour. In addition, the standard operating procedures will recommend interviewers to offer pauses for mothers during the interview. Privacy will be ensured.

Some of the specific questions to be addressed are:

- From woman's perspective: how do women feel about providing skin-to-skin care, starting immediately after birth? How do women feel about the extended stay in the facility and what support is available to ensure there is support in the home?
- From a community perspective: What support can they provide to the mother for the care of the baby? Who can serve as an appropriate surrogate to mothers for providing iKMC in each site according to their culture and how their availability at the time of birth can be ensured?
- From system perspective: how can the women be given appropriate care and comfort while they are in the hospital to provide KMC to their infants and to ensure their satisfaction with the care provided? How can space to accommodate mothers and infants remaining together be ensured in the M-SNCUs?
- What skills do health workers need to support mothers to provide iKMC?
- Where KMC has been practiced already, what are the challenges that the mothers face in providing continuous skin-to-skin contact and exclusive breastfeeding to their babies and how can they be resolved?
- If not being practiced, from the providers' perspectives what could be the anticipated challenges in implementation.

Discussions with other household members including men will be conducted to determine their perspectives and experience with the care of the preterm or LBW infant and the support they can provide to the mother. This will aid in the choice of surrogates and steps needed to ensure presence of surrogates at the time of birth and to ensure continued KMC in the home. This will help us to optimize health system strategies addressing women, families, and communities. Separate FGDs will be held with women and with men.

Compensation for participants involved in the formative research will be provided based on the local norms and standards in each setting. These participants may also be provided with light refreshment (such as a cold beverage and snack).

Interviews with health managers and health workers of different cadres (nurses, midwives, doctors, CHWs) across the networks of care (primary health centre, first level facility, second level and higher-level facility) to understand factors affecting the implementation of iKMC and continued KMC. This will help us to understand the current provision of early newborn care for preterm or LBW babies and explore the feasibility and acceptability of different components of the iKMC implementation model. Given that caring for women and babies born preterm or LBW requires a team-based approach across multiple cadres (CHWs, nurses, midwives, obstetricians, paediatricians), we will explore how hierarchies and gendered relations between cadres may influence care for both women and babies.

At the start of the interviews and group discussions, participants will be asked to confirm that they have received the information sheet and signed the consent form. IDIs are expected to last approximately 60 minutes, focus group discussions are expected to last approximately 90 minutes.

Both IDIs and group discussions will be conducted by researchers with experience in qualitative methods and in maternal and newborn health programmes.

As mentioned, data will be analyzed in parallel with data collection, monitoring for thematic data saturation. Interviews and discussions will be digitally recorded, and notes of each session will be taken, including descriptive and reflective information. All notes will be anonymized to ensure privacy and confidentiality of participants. Participants and sites will be given identifying numbers for reference. All data will be stored and backed up on secured password- protected system and will not be accessed nor shared with a third party without prior permission. See Section 4.3 for additional information.

The team will identify key themes emerging from the notes of the different activities and will report extracts to provide examples of specific issues. Themes identified will be mapped to the different domains of the Consolidated Framework for Implementation Research and to key areas related to iKMC intervention implementation, identifying key barriers and facilitators for iKMC implementation.

As mentioned, for programme learning activities discussions will be organized with different stakeholder groups to receive input on what is working and not working well in iKMC implementation. Instruments and processes will be adapted from the formative research. Assuming consensus in each of the population groups mentioned, we estimate five participants from each group to be interviewed for a total of up to 40 interviews during each 3-4 months cycle. The final number of interviews might vary according to consensus levels. At the start of the interviews, participants will be asked to confirm that they have received the information sheet and signed the consent form.

4.2.2 Model optimization outcome measurement

Birth weight of live births in iKMC implementing facilities, primary level birthing facilities and at homes: the evaluation team will collect birth weight data of live births in all health facilities in the district through periodic visits to these facilities. The number of preterm or LBW babies requiring admission to the level 2 M-SNCU will be documented based on the admission criteria for that unit (e.g., <1.8 kg). They will also record the date and time of birth for such LBW babies born in iKMC implementing facilities, as well as date and time of birth and of admission for babies born at lower-level facilities and at home.

The outcome measurement team will collect the data on the time of initiation of iKMC and who initiated iKMC through daily visits to newborn care units in iKMC implementing facilities in the district. For babies born at home or in a primary level facility and brought to iKMC implementing facility, information on the time of initiation of KMC will be ascertained from the mother or another caregiver and data will also be taken from the register in the primary level facility. Daily information on the hours of skin-to-skin contact will be collected by the evaluation team (by asking the mothers) while the baby is in the level 2 M-SNCU. Staff at the iKMC implementing facilities will record the time of initiation and duration of KMC in hospital records. Detailed information on definitions, numerators, and denominators for each outcome in the model optimization phase is described in Table 3.

The study team will train and supervise staff at the iKMC implementing facilities to record above mentioned information in the register accurately. Spot checks will be conducted by the study team to ensure quality of data collected in the iKMC implementing facilities. Ongoing monitoring and discussions by the WHO team will also include regular review of data.

Table 3. Definitions, numerators, and denominators of outcomes in model optimization phase

	Numerator and	Specific notes	Data collected by						
	denominator	to the indicator	Who	How and where					
Primary coverage outcomes									
Proportion of preterm or LBW newborns requiring care in the M-SNCU born in or brought to the iKMC implementing facility, within 24 hours of birth, who received iKMC.	Numerator: Number of preterm or LBW newborns who received iKMC (in an iKMC implementing facility) Denominator: Number of preterm or LBW newborns admitted in the M-SNCU born in or brought to the iKMC implementing facility, within 24 hours of birth (Expressed as a percentage)	A baby is considered to have received iKMC if: 1. Skin-to-skin contact is initiated within 2 hours after birth if the baby is born within the iKMC implementing facility, or if the baby is born outside the iKMC implementing facility, within 2	Outcome measurement team	By checking M- SNCU register / clinical records filled by routine staff in M-SNCU and interviews with mothers at M- SNCU					

	Numerator and	Specific notes	Data (collected by
	denominator	to the indicator	Who	How and where
		hours of reaching the iKMC implementing facility (who reach the facility within 24 hours of birth) and 2.Skin-to-skin contact is provided by a mother/surrogate for at least 8 hours per day during the stay in the level 2 M- SNCU hospital (average hours per day for the overall M-SNCU stay)		
Other outcomes				
Proportion of preterm or LBW infants who are transported to an iKMC implementing facility within 24 hours after birth among those referred to an iKMC implementing facility	Numerator: Number of preterm or LBW infants who are transported to an iKMC implementing facility within 24 hours after birth Denominator: Number of preterm or LBW infants* requiring referral to an iKMC implementing facility *Infants requiring referral born in birthing facilities or at home whose birth weight is known		Outcome measurement team	By checking M-SNCU register / clinical records filled by routine staff in M-SNCU At iKMC implementing facility when the baby is admitted Birth weight and or gestational age data will be collected from all birthing facilities for the denominator
Proportion of preterm or LBW infants on respiratory support (any oxygen or CPAP) who received skin- to-skin contact > 8 hours/day in the M-SNCU	Numerator: Newborn who received skin-to-skin contact > 8 hours/day in the M-SNCU Denominator: Preterm or LBW infants on respiratory support in the level 2 M-SNCU (Expressed as a percentage)		Outcome measurement team	By checking M- SNCU register / clinical records filled by routine staff in M-SNCU and interviews with mothers At M-SNCU

	Numerator and	Specific notes	Data (collected by
	denominator	to the indicator	Who	How and where
Proportion of preterm or LBW infants receiving KMC (8-24 hours of skin-to-skin contact and exclusively breastfed) in the 24 hours before discharge from the iKMC implementing facility	Numerator: Number of preterm or LBW infants receiving 8-24 hours of skin-to-skin contact and exclusively breastfed in the 24 hours before discharge Denominator: Number of preterm or LBW infants who admitted in the M-SNCU in the iKMC implementing facilities who are discharged alive (Expressed as a percentage)		Outcome measurement team	By checking hospital register / clinical records filled by routine staff i ward and interviews with mothers At iKMC implementing facility
Proportion of preterm or LBW infants exclusively breastfed at discharge	Numerator: Infants who are exclusively breastfed Denominator: Preterm or LBW infants requiring M-SNCU care born alive in or brought alive to the iKMC implementing facility i		Outcome measurement team	By checking hospital register / clinical records filled by routine staff i and interviews with mothers at iKMC implementing facility (discharge area)
Median age at putting the baby to breast for the first- time during M-SNCU stay (Expressed in median hours/days)	Median age in hours/days when a preterm or LBW infants is first put to mother's breast during M-SNCU stay		Outcome measurement team may cross-verify the information using the clinical records.	By registering data on all preterm or LBW infants admitted to M-SNCUs in CRF At iKMC implementing facility when the baby is admitted and interviews with mothers

We will use the standards for reporting implementation studies (StaRI)⁴⁷ statement to report on the design and development of the optimized implementation model development.

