3.5 The iKMC implementation model

3.5.1 Key components of the iKMC implementation model

Based on learnings from the iKMC trial coordinated by WHO, the iKMC (intervention) in this implementation study is defined as follows. A baby is considered to have received iKMC if:

- Skin-to-skin contact is initiated within 2 hours after birth if the baby is born within the iKMC implementing facility; if the baby is born outside, then within 2 hours of reaching the iKMC implementing facility (for those babies who reach the facility within 24 hours of birth)
- Continuous skin-to-skin contact is provided by a mother/surrogate for at least 8 hours per day during the stay in the level 2 M-SNCU (average hours per day for the overall M-SNCU stay)
- Support for early and exclusive breastmilk feeding is provided to the mother
- Required medical care for the mother and baby is provided without separation, as much as possible

An important infrastructural modification that is ideally needed for iKMC is the transformation of the level-2 SNCU to level 2 M-SNCU by allowing the mother or surrogate to stay with the baby 24 hours/7 days.

Intervention characteristics including its design have been described by the WHO iKMC study²¹, and the relative advantages and high-quality evidence of its efficacy in improving survival of preterm or LBW babies. In addition to the above, a minimum package of care for preterm and/or LBW babies requiring care in level 2 SNCUs will be provided (see Annex 1): (essential newborn care at birth, thermal control, KMC including continuous skin-to-skin contact for stable babies and exclusive breastmilk feeding, attention to hygiene and regular monitoring for all babies; and intravenous fluids, antibiotic therapy, and respiratory support including CPAP, if required). Core components of the intervention package include support to empower and enable the mother to take care of her baby and to ensure the appropriate care of the mother and baby, as described below:

Promotion and support for continuous skin-to-skin contact, initiated as soon as possible after birth

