3.6.2 Outcomes for the model optimization phase

The main outcome of the design and optimization phase will be development of *the optimized implementation models* that achieves a high coverage and quality of iKMC and establish the norm of zero separation between the mother and her newborn in the four participating countries.

This will be measured through a primary coverage outcome in a tracer indicator that captures the skin-to-skin component of iKMC i.e., initiation and duration of skin-to-skin contact.

Primary coverage outcome: Proportion of preterm or LBW newborns requiring care in level 2 M-SNCUs) born in or brought to the iKMC implementing facility, within 24 hours of birth, who received iKMC. This will be captured through a tracer indicator on initiation and duration of skin-to-skin contact.

A baby is considered to have received iKMC if:

- Skin-to-skin contact is initiated within 2 hours after birth if the baby is born within the iKMC implementing facility, or within 2 hours of reaching the iKMC implementing facility if the baby is born outside the iKMC implementing facility (who reach the facility within 24 hours of birth) and
- Continuous skin-to-skin contact is provided by a mother/surrogate for at least 8 hours per day during the stay in the level 2 M-SNCU hospital (average hours per day for the overall M-SNCU stay)

Quality outcomes:

Proportion of preterm or LBW infants who arrived to an iKMC implementing facility within 24
hours after birth among those born in a health facility who required referred at birth to an iKMC
implementing facility

^{*}These neonates (except deceased newborns) will be excluded from the study for outcome measurement purposes however all newborns will receive appropriate care in the iKMC implementing facility.

- Proportion of preterm or LBW infants on respiratory support (any oxygen or CPAP) who received skin-to-skin contact > 8 hours/day in the M-SNCU
- Proportion of preterm or LBW infants receiving KMC at discharge (8-24 hours of skin-to-skin contact and exclusively breastfed) in the 24 hours before discharge from the iKMC implementing facility
- Proportion of preterm or LBW infants who are exclusively breastfed at discharge
- Median age at putting the baby to the breast for the first-time during M-SNCU stay

Implementation outcomes:

In the model optimization phase, we will also monitor the following implementation outcomes, including experience of care by mothers/caregivers and newborns:

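### The respiratory-support indicator requires more than 8 hours of skin-to-skin contact a day, while the protocol's other duration criteria include 8, so an infant at exactly 8 hours meets the target but fails this indicator

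*Protocol*

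**What the plan says.** Section 3.6.2 lists, among the quality outcomes, the proportion of infants on any oxygen or CPAP "who received skin-to-skin contact > 8 hours/day in the M-SNCU". Table 3 in section 4.2.2 repeats the strict sign in the row's title and again in its numerator: "Numerator: Newborn who received skin-to-skin contact > 8 hours/day in the M-SNCU".

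The other duration rules include the value 8:

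- **iKMC received.** Section 3.6.2 has "Continuous skin-to-skin contact is provided by a mother/surrogate for at least 8 hours per day", and Table 3 has "provided by a mother/surrogate for at least 8 hours per day during the stay". Section 3.5.1 gives the same threshold and explains it as "average hours per day for the overall M-SNCU stay".
- **KMC at discharge.** The Table 3 numerator is "Number of preterm or LBW infants receiving 8-24 hours of skin-to-skin contact", combined with exclusive breastfeeding in the last 24 hours before discharge. Sections 3.6.2 and 3.7.5 and Table 4 use the same 8-to-24-hour range.
- **Delivery aim.** The description of the intervention in section 3.5.1 also sets a target of 8 hours or more per day.

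Section 3.7.5 carries the coverage and quality outcomes into the stepped-wedge phase unchanged.

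**The concern.** The protocol has one duration target, and 8 hours satisfies it. One indicator scores that target as a failure, and no reason is given for a stricter bar in infants on respiratory support. Since Table 3 is where numerators and denominators are fixed, a programmer would code the sign as printed.

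Exactly 8 hours is a plausible value. Section 4.2.2 has the evaluation team ask mothers daily about hours of contact, alongside staff records, and 8 is the figure being promoted. If answers come in whole hours, some infants will land on the boundary.

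The indicator is also used. Section 3.5.5 makes coverage and quality data the basis for optimizing the model at redesign workshops every 3 to 6 months, and the same indicator is then reported in the trial phase. A definitional slip here would lower the reported figure for a reason unrelated to care.

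**Working it through.** **Step 1: the rules side by side.** Only the duration part of each rule is compared.

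| Average hours per day | iKMC duration (8 or more) | KMC at discharge duration (8 to 24) | Respiratory support (> 8) |
|---|---|---|---|
| 7.9 | not met | not met | not met |
| 8.0 | met | met | **not met** |
| 8.1 | met | met | met |

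The rules part company at exactly 8.0 and nowhere else.

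**Step 2: is the sign deliberate or a slip?** It appears in all three places where the indicator is defined. Elsewhere, for example at the 1800 g limit in section 3.3, the protocol prints >= when the limit is included. As printed, the sign means strictly more than 8.

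**Step 3: how many infants could be affected?** The protocol gives no distribution of contact hours and no recording precision, so there is no stated figure to reproduce. The following is illustrative. Assumptions: each day's hours are normal with mean m and SD 3 h, rounded to whole hours and independent between days; the indicator is applied to the average over d days.

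For one day, the share at exactly 8 is Φ((8.5 − m)/3) − Φ((7.5 − m)/3).

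- m = 8: Φ(0.167) − Φ(−0.167) = 0.132
- m = 9: Φ(−0.167) − Φ(−0.5) = 0.125
- m = 10: Φ(−0.5) − Φ(−0.833) = 0.106

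For d days, the share is the probability that the d rounded values sum to 8d, found by convolving the one-day distribution:

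| Mean m | 1 day | 3 days | 5 days |
|---|---|---|---|
| 8 h | 13.2% | 7.7% | 5.9% |
| 9 h | 12.5% | 6.5% | 4.5% |
| 10 h | 10.6% | 4.0% | 2.0% |
| 14 h | 1.8% | about 0 | about 0 |

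At mean 9 h over 3 days, the same infants score 74.9% under at least 8 and 68.4% under > 8, a gap of 6.5 points. With finely recorded hours the gap goes to zero. Heaping of answers at 8 would widen it.

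**The case against.** Several points on the other side carry weight.

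- **Reading artefact.** A single-character greater-than-or-equal sign could have been turned into > when the PDF was read, and the same conversion would affect every occurrence. The >= seen elsewhere is two typed characters, so its survival does not settle the matter. This is a possibility without direct evidence. A glance at the source file would resolve it.
- **Passing two indicators and failing a third.** A reader might infer this, but the documents do not support it. Eight hours meets only the duration part. iKMC also requires that "Skin-to-skin contact is initiated within 2 hours after birth if the baby is born within the iKMC implementing facility", with a matching rule for outborn infants. KMC at discharge also requires exclusive breastfeeding and looks at the last 24 hours, often spent on another ward. Contact hours in the M-SNCU do not determine that result.
- **A false gap against other infants.** It is tempting to say the indicator would show infants on respiratory support getting less contact than the rest. The protocol specifies no such comparison. iKMC is a composite over all admitted infants, so it is not a like-for-like comparator.
- **Misdirected redesign.** The only numerical goal is the aspirational 80% iKMC coverage in section 3.5.5. No decision threshold hangs on this indicator, and qualitative findings are used to explain the results.
- **Data source and size.** Table 3 lists registers and clinical records as well as interviews, and section 4.2.2 provides for staff training and spot checks. Whole-hour reporting is therefore an assumption. So are the mean, the SD and the averaging over days, because this indicator states no averaging rule. At a mean of 14 h the effect almost disappears.

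These objections limit the consequences. The mismatch in the text remains.

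**Conclusion.** The point holds as a narrow inconsistency in a scoring rule. An infant on oxygen or CPAP with exactly 8 hours a day meets the protocol's duration target and is scored as a failure on the respiratory-support indicator. Only this value and only these infants are affected.

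The effect on the reported proportion cannot be derived from the protocol. Under whole-hour reporting with mean 8 to 10 h and SD 3 h it runs from about 2 to 13 percentage points, depending on the number of days averaged. With fine recording, or with typical contact well above 8 hours, it is close to nothing.

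A reader might infer that headline results are at risk. They are not: neonatal mortality, primary iKMC coverage and the sample size do not use this cut-off. The correction is minor but worth making, because the rule as written misclassifies infants exactly at target on an indicator used in both phases.

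**What to change.** Reconcile the indicator's scoring cut-off with the protocol's own definition of at least 8 hours per day. The strict sign occurs three times: once in the quality outcomes of section 3.6.2, and in both the title and the numerator of the respiratory-support row of Table 3. Check the source file first, in case the sign there already includes 8. If a stricter cut-off for these infants is intended, the protocol should say so and give the reason.

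The cost is one symbol in three places if done before data are scored. Done later, it means re-scoring the indicator and restating any figures already reported. The change affects counting only and alters nothing in the care given.
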